9.6.3 Laboratory Test Results

Laboratory parameters will be summarized using descriptive statistics, by postdose shifts relative to baseline, and a summary of subject incidence of clinically significant values.

For hematology, chemistry, and other laboratory parameters, the baseline values and changes from baseline values will be summarized descriptively.

For the summary of changes from baseline values, subjects without a baseline and/or post-baseline value will be excluded; values from both scheduled and unscheduled

assessments will be included. Laboratory results from samples taken > 30 days after the last administration of protocol therapy will be excluded from all laboratory summaries.

Laboratory test results will be graded using the NCI CTCAE (Version 4.03). Shifts in laboratory toxicity grades to outside the normal range will be evaluated for selected laboratory parameters (1. hematology analytes in decreasing direction: Hemoglobin, Lymphocyte, Absolute Neutrophil Count, Platelet, WBC; 2. chemistry analytes in increasing direction: Alanine Aminotransferase, Aspartate Aminotransferase, Total Bilirubin, Corrected Calcium, Serum Creatinine, Potassium, Sodium, Magnesium; 3. chemistry analytes in decreasing direction: Albumin, Corrected Calcium, Potassium, Magnesium, Phosphorus, Sodium) by assessing the maximum increase and/or decrease observed during the course of study treatment relative to the baseline toxicity grade.

The subject incidence of Grade 3 and 4 hematological laboratory abnormalities (including neutropenia, thrombocytopenia, and anemia) will be provided by treatment group.

The subject incidence of Grade 3 and 4 nonhematological toxicities (including liver function test [LFT], CrCl) will be provided by treatment group.

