7.3.15 Laboratory Assessments

Laboratory tests including hematology and serum chemistries during scheduled visits will be performed at a central laboratory [REDACTED], and at the local laboratory thereafter. In the absence of central laboratory values, all

local laboratory values must be recorded in the eCRF. Subjects must fast for at least 9 hours before screening hematology and serum chemistries. If central laboratory results for lactate dehydrogenase (LDH), bilirubin, AST, and potassium are not reported/available at screening, local laboratory results may be utilized if completed within the screening window. Screening coagulation tests will be done at local laboratories. Post-enrollment, laboratory samples may be collected and analyzed by local laboratories if immediate results are necessary for management of treatment-emergent adverse events or dosing determination. Evaluation of lab results for dose determination as required per Schedule of Assessments must be documented prior to dosing in each cycle. Any local lab values that lead to dose modification decisions must be recorded in the eCRF. Any local laboratory results that fulfill \geq grade 3 values per Common Terminology Criteria for Adverse Events (CTCAE) must be recorded in the eCRF.

For cycle 1 day 1, hematology and serum chemistry panel from screening may be used if within 14 days of day 1. For subsequent visits in cycle 1, hematology and chemistry may be completed up to 72 hours prior to scheduled dose weekly for cycle 1. Starting in cycle 2, only day 1 is required.

Subjects who do not have a prior medical history of hepatitis B or who have not had testing conducted within the previous 12 weeks, will be tested locally for HBsAg, anti-HBs, and anti-HBc at their next visit. In addition, subjects with a clinical history of hepatitis B infection or who test positive for HBV serologies will be monitored closely for signs and symptoms of hepatitis B and will have local HBV DNA testing performed at their next visit and then every 12 weeks (\pm 2 weeks) or more frequently if clinically indicated through follow-up visit 1. Subjects in arm1 (KdD) will continue to be monitored and tested for 6 months following the last dose of daratumumab.

[Table 15](#) below outlines the specific analytes that will be assessed during the study.

Table 15. Laboratory Analyte Listing

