9.1 General Considerations

The efficacy analyses of PFS and key secondary endpoints will be conducted on the full analysis set. Treatment effects in efficacy endpoints will be evaluated and compared between KdD vs Kd.

In principle, summary statistics including mean, standard deviation, median, first and third quartiles, will be provided for continuous variables. Frequency and percentage will be summarized by treatment arm for binary and categorical variables. Proportions and

the corresponding 95% CI will be based on **Clopper-Pearson Method** and the treatment comparison will be based on Cochran-Mantel-Haenszel test. Exact tests will be considered for subgroup analyses when the cell size is considered small. Time to event endpoints will be estimated using the Kaplan-Meier (K-M) method. Stratified log-rank test statistics and associated p-values will also be calculated. Hazard ratios will be estimated using stratified Cox proportional hazards models. **Stratification factors include original International Staging System (ISS) stage (Stage 1 or 2 vs Stage 3) at screening; prior proteasome inhibitor exposure (yes vs no); number of prior lines of therapy (1 vs ≥ 2); prior cluster differentiation antigen 38 (CD38) antibody therapy (yes vs no). A stratification factor will not be used if any level of the factor contains less than 5% of the whole population.**

The adequacy of the proportional hazard assumption will be assessed using the plot of the logarithm of the estimated hazard function based on the Kaplan-Meier method against the logarithm of time-to-event endpoints. The scaled Schoenfeld residuals by time plot will be examined for evidence of a non-zero correlation, which indicates non-proportionality. In addition, a treatment-by-time(log) interaction test will be performed using a Cox model with stratification factors.

For PFS, response and disease progression will be determined by an IRC in a blinded manner. In addition, response and disease progression outcomes will be determined locally by investigators in an unblinded manner and centrally by the sponsor using a validated computer algorithm (Onyx Response Computer Algorithm, ORCA) in a blinded manner. The primary analysis of PFS will be based on IRC assessed outcomes; the timing will be event driven and will happen when approximately 188 PFS events are reached. The PFS outcomes assessed by the investigators as well as by ORCA will serve as supportive analyses of PFS.

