9.6.4 Vital Signs

Vital signs including systolic/diastolic blood pressure, pulse, respiratory rate, and temperature will be summarized by changes from baseline values for each treatment group using descriptive statistics.

For the summary of changes from baseline by visit, subjects without a baseline and/or post baseline value will be excluded; values from unscheduled assessments will be excluded. **Subjects with missing data for a scheduled assessment time point will be excluded from the graphical summary for that time point.** Vital sign results taken > 30 days after the last administration of protocol therapy will be excluded from all vital sign summaries.

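### Laboratory change-from-baseline summaries pool unscheduled, largely event-triggered values with scheduled ones, although the endpoint is tied to scheduled assessments

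*SAP*

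**What the plan says.** **Laboratory summary.** SAP 9.6.3 excludes subjects without a baseline or follow-up value and then admits every other value: "post-baseline value will be excluded; values from both scheduled and unscheduled", the sentence continuing that both are included. It does not say that the summary is by visit. It gives no visit window, no rule of one value per subject per time point, and no rule for combining local with central results. SAP 9.1 states that "summary statistics including mean, standard deviation, median, first and third quartiles, will be provided for continuous variables", so means are among the planned statistics.

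**Endpoint.** The synopsis, Protocol 10.1.1.2 and SAP 2.1 all list safety laboratory values, LVEF, the FEV1/FVC ratio and vital signs together as one secondary endpoint, evaluated at the scheduled assessments.

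**Neighbouring safety summaries.** For by-visit changes in vital signs, SAP 9.6.4 says "values from unscheduled assessments will be excluded". SAP 9.7.4 summarises echocardiograms by visit and reports unscheduled scans separately, linked to the adverse events that prompted them. SAP section 10 lists changes to subgroups only.

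**Where off-schedule local values come from.** Protocol 7.3.15 allows that after enrollment "laboratory samples may be collected and analyzed by local laboratories if immediate results are necessary for management of treatment-emergent adverse events", or for a dosing decision. It has three recording rules:
- "Any local lab values that lead to dose modification decisions must be recorded in the eCRF"
- local results that meet or exceed "grade 3 values per Common Terminology Criteria for Adverse Events (CTCAE) must be recorded in the eCRF"
- "In the absence of central laboratory values, all" "local laboratory values must be recorded in the eCRF" (one sentence, broken across a page)

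**The concern.** A mean change from baseline is useful when every subject contributes at the same planned times. Scheduled draws do this. An urgent local draw does not: on the protocol's own description it happens because something is already wrong or a dose is in doubt. If these values go into the same mean, two things follow. The mean can move toward toxicity, and a subject with several urgent draws counts several times while a well subject counts once per visit. From cycle 2 only day 1 laboratory tests are required, so a subject with two extra draws in a cycle would supply 1 + 2 = 3 records where another supplies 1.

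What is at stake is the reading of a named secondary safety endpoint in an open-label comparison. The summary would describe something other than the endpoint as defined, and SAP section 10 does not declare the difference.

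**Working it through.** The plan states no figure on this point, so there is nothing to reproduce. The check is a comparison of texts followed by an illustration on assumed inputs.

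**Step 1: the texts.** The endpoint covers scheduled assessments, and SAP 9.6.3 adds unscheduled values. For two other components of the same endpoint line (vital signs in SAP 9.6.4, LVEF in SAP 9.7.4), unscheduled values are either left out or reported apart. No reason is given for treating laboratory values differently.

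**Step 2: which values are at issue.** Event-triggered drawing is established by Protocol 7.3.15. Two of its recording rules (dose modification; grade 3 or higher) add selection toward abnormal results. The third asks for all local values when central values are absent, and so works the other way.

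**Step 3: direction and possible size.** All inputs here are assumptions except the grade 3 platelet limit (below 50 x 10^9/L, SAP Table 5). Baseline is 200; scheduled values have mean 160 and SD 60; unscheduled values have SD 50 and mean 60, 90, 120 or 160. The unscheduled share f of all tests is 2%, 5% or 10%. Values were simulated with a floor of 5. The scheduled-only mean change is -39.9.

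With every unscheduled value recorded, shift = f x (unscheduled mean - scheduled mean). For example, 0.02 x (120 - 160) = -0.8. At f = 0.10 and mean 60 the formula gives 0.10 x (60 - 160) = -10.0; the floor at 5 reduces this to -9.7.

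With only grade 3 or higher values recorded, let p be the fraction of unscheduled values below 50 and w = f x p. Then shift = [w / (1 - f + w)] x (mean of recorded values - scheduled mean). At mean 60 and f = 0.10, p = 0.42, w = 0.042, and the weight is 0.042 / 0.942 = 0.045.

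| Unscheduled mean | Shift, all recorded (f = 2% / 5% / 10%) | Shift, grade 3+ only (f = 2% / 5% / 10%) |
|---|---|---|
| 60 | -1.9 / -4.8 / -9.7 | -1.2 / -3.0 / -6.2 |
| 90 | -1.4 / -3.5 / -6.9 | -0.6 / -1.5 / -3.1 |
| 120 | -0.8 / -2.0 / -4.0 | -0.2 / -0.6 / -1.2 |
| 160 (same as scheduled) | 0.0 / 0.0 / 0.0 | 0.0 / -0.1 / -0.2 |

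**Step 4: reading the table.** When draws are prompted by toxicity (means 60 to 120), the shift is larger with full recording (-0.8 to -9.7) than with grade 3+ recording (-0.2 to -6.2), because more unscheduled values enter. The main driver is therefore why the sample was taken; the recording rule comes second. When unscheduled values resemble scheduled ones, the shift all but disappears.

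**The case against.** The other side has several fair points.

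- **Recording.** A reader might infer that only severe or dose-changing local results reach the database. The documents do not support this. All local values are required when central ones are absent, and an urgent draw with no paired central sample can be read as such a case. The triggers are minimum requirements, and unscheduled central results are not subject to them. Step 4 shows that the concern does not depend on selective recording.
- **Opposite rules.** A reader might infer that SAP 9.6.3 and 9.6.4 contradict each other on the same display. SAP 9.6.4 speaks of changes by visit and SAP 9.6.3 does not, so strictly they describe different displays. What stands is that the laboratory summary is under-specified and departs from the endpoint definition.
- **Difference between arms.** A reader might infer that KdD is affected more because of its day 22 infusions. Table 11 schedules cycle 1 day 22 hematology and chemistry in both arms, and longer treatment adds scheduled draws as well. An imbalance is possible but not shown.
- **Local values in the summary.** SAP 8.2 names the central laboratory as the source of laboratory data. Local-laboratory forms do exist (SAP section 5, last known alive date; footnotes to SAP Table 5), and SAP 9.6.3 does not exclude them, but their entry into this summary is not explicit.
- **Versions.** The SAP follows protocol amendment 4, while the recording text is from amendment 6. Whether that text was the same earlier cannot be confirmed. The endpoint argument does not need it.
- **Weight.** Toxicity is carried mainly by the worst-grade shifts and grade 3/4 incidence, which this does not harm. That stands and limits the severity.

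**Conclusion.** The point holds and is minor. SAP 9.6.3 brings unscheduled values into a summary whose endpoint is defined at scheduled assessments, without declaring the change. Because Protocol 7.3.15 ties post-enrollment local draws to adverse events and dosing decisions, following the rule as written can shift mean changes toward toxicity and gives more weight to subjects with repeated draws. Medians and quartiles are less affected.

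The size is unknown. The range of 0 to -9.7 x 10^9/L for platelets rests wholly on assumed distributions, an assumed unscheduled share of 2% to 10%, and one mean pooled over records, which the SAP does not specify. It shows direction and plausibility; it does not estimate what this trial would show. The documents do not support a stated bias in either arm or a false difference between arms. No test is planned on these summaries, so no inferential conclusion is at risk.

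**What to change.** In SAP 9.6.3, restrict the change-from-baseline summaries to scheduled assessments, presented by visit. Use the central value, or the local value when the scheduled test was done locally or the central value is missing. The local provision is needed because Protocol 7.3.15 moves scheduled testing to local laboratories after a certain point; a central-only filter would drop those later scheduled results.

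State in the same place that all scheduled and unscheduled values continue to feed the worst-grade shift tables and the grade 3/4 incidence, so that no severe value is lost from the report.

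The cost is a sentence or two in the SAP and a filter in the laboratory summary program. The downside is that some extra values drop out of the descriptive means.

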- time to next treatment
- TTP
- time to response
- sustained MRD[-]CR (defined as the proportion of subjects that maintain MRD[-]CR for 12 months or more after achieving MRD[-]CR status)
- CRR (defined as the proportion of best overall response of sCR or CR)
- MRD[-] rate
- electronic clinical outcome assessments (eCOAs): quality of life questionnaire – core 30 items (QLQ-C30) Global Health Status/Quality of Life (QoL) measured by European Organisation for Research and Treatment of Cancer (EORTC) QLQ-C30 version 3 questionnaire
- subject incidence of treatment-emergent adverse events
- safety laboratory values, left ventricular ejection fraction (LVEF), forced expiratory volume in 1 second (FEV1)/forced vital capacity (FVC) ratio, and vital signs at each scheduled assessment

Study Design: This is a phase 3 multicenter, open-label, randomized study in subjects with relapsed or refractory multiple myeloma (RRMM) who have received 1 to 3 prior therapies.

Subjects will be randomized in a 2:1 ratio to 1 of 2 arms:

- Arm 1: KdD
- Arm 2: Kd

Randomization will be performed using an interactive voice/web response system (IxRS) and subjects will be stratified based on the following criteria: Original International Staging System (ISS) stage (variables: albumin and beta 2 microglobulin; strata: Stage 1 or 2 vs Stage 3) at screening, prior proteasome inhibitor exposure (yes vs no), number of prior lines of therapy (1 vs ≥ 2), and prior cluster differentiation antigen 38 (CD38) antibody therapy (yes vs no).

Subjects will receive the **study** treatment determined by randomization [REDACTED] or until confirmed disease progression, unacceptable toxicity, withdrawal of consent, or death (whichever occurs first). No crossover between the treatment arms will be allowed. All subjects will be assessed for multiple myeloma disease response according to the IMWG-URC using central laboratory test results every 28 ± 7 days. [REDACTED] disease response assessments will be performed every 28 ± 7 days until confirmed progressive disease (PD).

Following progression or discontinuation of study drug(s), subjects will have 1 follow-up visit (30 days [+ 3] after last dose of all study drug[s]). **After disease progression**, data on survival status and subsequent antimyeloma therapy will be gathered at [REDACTED].

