FISH = fluorescence in-situ hybridization; HBV = hepatitis B virus; IAT = indirect antiglobulin test; K = carfilzomib; LTFU = long-term follow-up; LVEF = left ventricular

ejection fraction; MRD = minimal residual disease; PD = progressive disease; ██████████ PFT = pulmonary function test; PK = pharmacokinetics;

QTc = corrected QT (interval); SAE = serious adverse event.

^a Follow-up occurs: 30 days (+ 3) after the last administration of all study drug(s).

Table 12. Schedule of Disease Assessments

Assessment	Screening	Every 28 Calendar Days ^a (Starting From C1D1)	If Clinically Indicated	To Confirm PD	Notes
Disease Assessments					
Bone marrow sample for FISH and MRD[-]:	X	(X)			See Section 7.3.21.2 for additional timing details regarding FISH and MRD[-] assessments. Samples for MRD analysis are not required [REDACTED]
Bone lesion assessment	X		X	X	Within 30 days prior to randomization; will be repeated if worsening clinical symptoms suggest PD, or as clinically indicated.
Plasmacytoma evaluation	(X)	(X)	X	X	Will be done at screening only if clinically suspected. Screening evaluation may be done within 30 days prior to randomization, if performed as a part of standard of care. Assessment will be performed locally every 28 days (for physical exam) or every 12 weeks (for radiological exam).
SPEP/UPEP/immunofixation	X	X			Screening values may be used if within 14 days prior to C1D1. Post C1D1, UPEP and urine immunofixation will be measured every disease assessment.
SFLC	X	X			

(X) = Parentheses indicate that the particular test is situational at that time point, as specified in the respective notes.

CxDx = Cycle X day X; **DCO = data cutoff**; FISH = fluorescence in-situ hybridization; MRD = minimal residual disease; **OS = overall survival**; PD = progressive disease; PR = partial response; SFLC = serum free light chain; SPEP = serum protein electrophoresis; UPEP = urine protein electrophoresis.

^a [REDACTED], disease assessment should be performed every 28 ± 7 days until PD regardless of cycle duration including dose delays. Subjects who discontinue treatment prior to PD, but remain on study are required to complete the following assessments every 28 ± 7 days until PD. [REDACTED]

Table 13. Dosing Schedule - Arm 1 (KdD)

Investigational Products and Other Protocol-required Therapies	Dosing Cycle Day							Notes
	1	2	8	9	15	16	22	
IV predose and postdose hydration (for carfilzomib as needed)								

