7.2.4 Follow-up Visits

The following procedures will be completed during the follow-up visit (30 days [+ 3] after last dose of all study drug(s) as listed in the Schedule of Assessments ([Table 11](#)).

Details of these procedures can be found in Section [7.3](#).

- Adverse event/serious adverse event reporting
- Concomitant medications
- Physical examination as per standard of care
- ECOG PS
- Vital signs
- Laboratory assessments: hematology, chemistry, and **HBV DNA testing**
- **Subjects with a known history of HBV infection or who test positive for HBV serologies may require additional testing (see Sections [6.7.1](#) and [7.3.15](#))**
- Subsequent antimyeloma therapy
- Optional assessments (consent must be obtained): pharmacogenetics sample (bone marrow aspirate) and biomarker assessment (plasma and serum)

[REDACTED], subjects who discontinue treatment prior to PD, but remain on study are required to complete the following assessments every 28 ± 7 days until PD as listed in [Table 12](#) (these visits may overlap with follow-up visits that are scheduled based on last dose of all study drug[s]):

- Disease assessments: SPEP/UPEP/IFE, SFLC (analyzed by central laboratory)

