9.2 Safety Event Reporting Procedures

9.2.1 Adverse Events

9.2.1.1 Reporting Procedures for Adverse Events That Do Not Meet Serious Criteria

The investigator is responsible for ensuring that all adverse events observed by the investigator or reported by the subject that occur after signing of ICF through 30 days after the last dose of study treatment or the follow-up visit (whichever is later) are reported using the Event CRF. **All adverse events of HBV reactivation for arm 1 subjects with evidence of positive HBV serology or known medical history of HBV infection are required to be reported through end of study.**

The investigator must assign the following adverse event attributes:

- adverse event diagnosis or syndrome(s), if known (if not known, signs or symptoms),
- dates of onset and resolution (if resolved),
- severity (and/or toxicity per protocol),
- assessment of relatedness to investigational product(s) or other protocol-required therapies, and
- action taken.

The adverse event grading scale used will be the Amgen adverse event standard grading score; Common Terminology Criteria for Adverse Events (CTCAE). The grading scale used in this study is described in [Appendix A](#).

The investigator must assess whether the adverse event is possibly related to the investigational product(s). This relationship is indicated by a “yes” or “no” response to the question: Is there a reasonable possibility that the event may have been caused by the investigational product(s)?

The investigator must assess whether the adverse event is possibly related to any study-mandated activity (eg, administration of investigational product, protocol-required

therapies, use of medical device(s) and/or procedure (including any screening procedure(s)). This relationship is indicated by a “yes” or “no” response to the question: “Is there a reasonable possibility that the event may have been caused by a study activity (eg, administration of investigational product, protocol-required therapies, use of medical device(s)), and/or procedure”?

The Investigator is expected to follow reported adverse events until stabilization or reversibility.

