Heart rate	number of cardiac cycles per unit of time
HR	hazard ratio
ICH	International Council for Harmonisation
Interactive Voice Response (IVR)	telecommunication technology that is linked to a central computer in real time as an interface to collect and process information.
Interactive Web Response (IWR)	web based technology that is linked to a central computer in real time as an interface to collect and process information.
IRC	Independent Review Committee

Abbreviation or Term	Definition/Explanation
ISS	International Staging System
ITT	Intention-to-Treat
IMWG-URC	International Myeloma Working Group-Uniform Response Criteria
IxRS	interactive voice/web response system
KdD	20/56 mg/m ² twice weekly carfilzomib, dexamethasone, and daratumumab
Kd	20/56 mg/m ² twice weekly carfilzomib and dexamethasone
K-M	Kaplan-Meier
LTFU	long-term follow-up
LVEF	left ventricular ejection fraction
MRD[-]CR	minimal residual disease negative-complete response; defined as achievement of CR (includes sCR) per International Myeloma Working Group-Uniform Response Criteria (IMWG-URC) and MRD[-] status as assessed by NGS (at a 10 ⁻⁵ level)
NGS	Next-Generation sequencing
ORCA	Onyx Response Computer Algorithm
ORR	overall response rate
OS	overall survival
PD	progressive disease
PDn	pharmacodynamics
PK	pharmacokinetic
PFS	progression free survival
PR	partial response
PS	performance status
QLQ-C30	quality of life questionnaire – core 30 items
QLQ-MY20	quality of life questionnaire - myeloma 20 items
QoL	quality of life
QT interval	QT interval is a measure of the time between the start of the Q wave and the end of the T wave in the heart's electrical cycle as measured by ECG
QTc	QT interval corrected for heart rate using accepted methodology
R-ISS	Revised International Staging System
RRMM	relapsed or refractory multiple myeloma
SAP	statistical analysis plan
sCR	stringent complete response
SNPs	single nucleotide polymorphisms
VGPR	very good partial response
WBC	white blood cells

1. Introduction

The purpose of this Statistical Analysis Plan (SAP) is to provide details of the statistical analyses that have been outlined within the protocol amendment 4 for study 20160275, (carfilzomib) dated **17 May 2019**. The scope of this plan includes the primary **analysis for PFS, interim** and final analyses **for OS** that are planned and will be executed by the Amgen Global Biostatistical Science department unless otherwise specified.

2. Objectives, Endpoints and Hypotheses

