3.1 Study Design

This is a phase 3 multicenter, open-label, randomized study in subjects with relapsed or refractory multiple myeloma (RRMM) who have received 1 to 3 prior therapies.

Subjects will be randomized in a 2:1 ratio to 1 of 2 arms: Arm 1: KdD vs. Arm 2: Kd.

Randomization will be performed using an interactive voice/web response system (IxRS) and subjects will be stratified based on the following criteria: 1) International Staging System (ISS) stage (Stage 1 or 2 vs Stage 3) at screening, 2) prior proteasome inhibitor exposure (yes vs no), 3) number of prior lines of therapy (1 vs ≥ 2), and 4) prior cluster differentiation antigen 38 (CD38) antibody therapy (yes vs no).

Subjects will receive the treatment determined by randomization for a maximum of 4 years or until confirmed disease progression, unacceptable toxicity, withdrawal of consent, or death (whichever occurs first). No crossover between the treatment arms will be allowed. All subjects will be assessed for multiple myeloma disease response according to the IMWG URC (Kumar et al, 2016) using central laboratory test results every 28 ± 7 days. Disease response assessments will be performed every 28 ± 7 days until confirmed progressive disease (PD), irrespective of cycle duration including dose delays or treatment discontinuation.

Following progression or discontinuation of study drug(s), subjects will have 2 follow-up visits (30 days [+ 3] and 8 weeks [± 7 days] after last dose of all study drug[s]) and then remain in long term follow up (LTFU) where data on survival status **and subsequent antimyeloma therapy** will be gathered every 12 weeks ± 2 weeks.

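### The SAP's 30-day cut-off for laboratory and vital-sign summaries leaves out follow-up visits done in window on days 31 to 33

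*SAP*

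**What the plan says.** SAP 9.6.3 closes the laboratory window with "Laboratory results from samples taken > 30 days after the last administration of protocol therapy will be excluded from all laboratory summaries". SAP 9.6.4 does the same for vital signs: "Vital sign results taken > 30 days after the last administration of protocol therapy will be excluded from all vital sign summaries". Neither section makes an exception for a scheduled visit done within its window.

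The current protocol gives one post-treatment visit. The Synopsis states that "subjects will have 1 follow-up visit (30 days [+ 3] after last dose of all study drug[s", and the footnote to Table 11 in Protocol 7.1 reads "Follow-up occurs: 30 days (+ 3) after the last administration of all study drug(s". Table 11 and Protocol 7.2.4 place hematology, chemistry and vital signs at this visit (7.2.4 begins its laboratory line "Laboratory assessments: hematology, chemistry, and").

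The SAP carries the same window in its own design section, 3.1: "subjects will have 2 follow-up visits (30 days [+ 3] and 8 weeks". The second visit appears there because the SAP describes analyses "outlined within the protocol amendment 4 for study 20160275", whereas the current protocol is Amendment 6 and has dropped it.

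Safety laboratory values and vital signs at the scheduled assessments are additional secondary endpoints (Protocol 10.1.1.2; SAP 2.1).

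**The concern.** The earliest day on which the follow-up visit may be done in window is the last day that the summaries accept. A site that follows the protocol and sees the subject one to three days later, as the window allows, produces results that the SAP then leaves out. The follow-up values that remain come from subjects who happened to attend on day 30, a selection made by calendar and not by any clinical or statistical criterion.

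At stake is the usefulness of the post-treatment part of the safety summaries: change from baseline in laboratory values, incidence of grade 3 and 4 laboratory abnormalities, and vital signs by visit. From cycle 2 onward, Table 11 schedules hematology and chemistry only on day 1 of the cycle and at follow-up visit 1, and Protocol 7.2.3 places assessments before dosing. For a subject who stops part-way through a later cycle, follow-up visit 1 is therefore the next scheduled laboratory sample after that cycle's doses.

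**Working it through.** No sample-size, power or alpha figure is involved. The check compares two sets of days, with day = assessment date minus date of last dose.

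**Inputs**
- Visit window, 30 days (+3): Protocol Synopsis, Table 11 footnote and 7.2.4; SAP 3.1. Permitted days are 30, 31, 32 and 33, so 33 − 30 + 1 = 4 days.
- Retention rule: SAP 9.6.3 and 9.6.4. A value is kept if day ≤ 30 and left out if day > 30.

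**Current rule**

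| Visit day | In protocol window | In SAP summaries |
|---|---|---|
| 30 | yes | yes |
| 31 | yes | no |
| 32 | yes | no |
| 33 | yes | no |

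Kept: 1 of 4 permitted days. Left out: 3 of 4.

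**Day counting.** Sections 9.6.3 and 9.6.4 do not say how days are counted. The time-to-event formulas in SAP Section 5 add 1 to the date difference. If that convention were carried over, a visit 30 calendar days after the last dose would count as day 31, and all 4 permitted days would be left out. The range is therefore 3 of 4 to 4 of 4, with 3 of 4 under a plain date difference.

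**The 8-week visit in SAP 3.1.** At 8 weeks ± 7 days it falls on days 56 − 7 = 49 to 56 + 7 = 63. All of these exceed 30, so results from that visit would not replace the ones left out.

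**With a cut-off of more than 33 days.** Days 30 to 33 all satisfy day ≤ 33, so 4 of 4 permitted days are kept. A visit on day 34 or later, which is out of window, stays out.

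**The case against.** The strongest defence is that 30 days is a consistent convention in this SAP. Treatment-emergent adverse events end no later than 30 days after the last dose (Section 5), deaths are split at 30 days (9.6.2), and Protocol 7.3.4 records adverse events and concomitant medications to 30 days. On that view the limit defines an on-treatment period, and moving it for laboratory and vital-sign data alone creates a new mismatch: a day-32 laboratory value would be summarised, while an adverse event starting that day would not be treatment-emergent. This stands as a cost of the change. It explains the choice of number, but it does not give the in-window follow-up visit any place in the summaries.

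Several stronger readings are tempting, and the documents do not support them:
- **That 75% of follow-up results are lost.** Three of four permitted days is not three of four subjects. A 75% loss needs an even spread over the four days; if half attended on day 30 the loss would be 50%. Neither pattern is documented.
- **That the data are thrown away.** They are collected and only left out of summaries. Adverse events found at the visit remain reportable, since Protocol 9.2.1.1 runs "through 30 days after the last dose of study treatment or the follow-up visit (whichever is later", and SAP 9.6.2 lists all adverse events, treatment-emergent or not.
- **That Protocol 9.2.1.1 proves the SAP wrong.** It is a collection rule. Collecting for longer than one analyses is not in itself an error.
- **That toxicity-grade shift tables are distorted.** SAP 9.6.3 bases them on the largest change while on study treatment, so a day-31 to day-33 sample would add little or nothing.
- **That many subjects have no other laboratory value after their last doses.** Protocol 7.3.15 allows local samples for managing adverse events or dosing. It requires recording of local values that are grade 3 or higher or that lead to dose modification. SAP 9.6.3 uses unscheduled values, which count if taken by day 30. The documents give no number of subjects without one.

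**Conclusion.** The conflict is real and lies within the SAP as well as between the SAP and the protocol. As written, the rule leaves out compliant follow-up visits on 3 of the 4 permitted days, assuming days are counted as a plain date difference. The number of subjects or results affected cannot be derived from the documents.

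The consequence is limited to descriptive safety output: laboratory change from baseline, grade 3 and 4 laboratory incidence, and by-visit vital signs. The vital-sign summary is the more exposed, because 9.6.4 also excludes unscheduled values from the by-visit changes. PFS, the key secondary endpoints and the type I error rate are unaffected, and the rule is the same in both arms. It is worth correcting because a stated rule gives a worse result than a nearly free alternative, not because any main conclusion of the trial depends on it.

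**What to change.** In SAP 9.6.3 and 9.6.4, change the exclusion to results taken more than 33 days after the last administration of protocol therapy, and state that days are counted as assessment date minus last dose date. This admits every in-window follow-up visit and no later one.

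A cut-off set at the later of 30 days or the follow-up visit would be less suitable. It has no upper limit, so a late, out-of-window visit could stretch the summary period, possibly past the start of subsequent antimyeloma therapy.

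The cost is two sentences and one programming cut-off. The laboratory and vital-sign window becomes up to 3 days longer (33 − 30) than the treatment-emergent adverse event window in SAP Section 5, equally in both arms. The SAP should note that difference, or present the in-window follow-up visit as its own row so that a strict 30-day summary remains available beside it.
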